Assessment of the sensitivity of the hypothalamic GnRH pulse generator to estradiol and progesterone inhibition in early pubertal girls (JCM026)

physical, screening blood tests) occurs immediately thereafter. Participants generally begin the main part of the study within 1-2 months of the screening visit.

Do you plan to enroll your own students, patients, staff, employees? Yes.

Do you plan to enroll students, patients, staff, employees of any of the other personnel listed on this protocol? Yes

Do you plan to enroll yourself or any other personnel listed on this protocol? No

If yes, which groups? Subjects may be recruited from Dr. [name]'s, Dr. [name]'s, Dr. [name]'s, Dr. [name]'s, and Dr. [name]'s clinical practices. However, Drs. [name], [name], rarely if ever see early pubertal girls in their clinics. It is also possible that the children of our clinic patients, students, or employees may be enrolled. We will not enroll children of study investigators.

If yes, explain how these potential subjects will be recruited to avoid the appearance of coercion.

Patients who appear to be appropriate candidates for this study will be made aware that they may qualify for participation in the study. If they express interest, we will offer a very brief explanation of what is involved. If the patient continues to express interest, we will give them our research coordinator's contact information. In keeping with our mandate as physicians, we will discuss the study only in instances where potential participation would not be harmful to the patient (e.g. in cases where temporarily withholding customary treatments is expected to have no harmful effects). Subjects will be informed that their participation in the study is entirely voluntary and their decision whether or not to participate will have no effect on their current or future medical care.

Biomedical Research

List what will be done in this protocol:

All procedures performed in this protocol are being done solely to answer a research question and generate generalizable knowledge.

Outpatient Screening

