If the screening tests show that the subject is eligible for the study, she will be given oral iron supplementation at a dose of 1-2 mg/kg for 30 days to help prevent anemia during and after the study. Subjects weighing \leq 36 kg will be given 300-325 mg oral ferrous gluconate daily (containing 36 mg of elemental iron); subjects weighing >36 kg will be given 300-325 mg oral ferrous gluconate twice daily. The admission can take place any time during or after the iron supplementation.

If overnight admission is scheduled to occur greater than one month after the most recent hemoglobin (such as that obtained during screening), a hemoglobin will be repeated 2-5 days before the overnight admission. Documentation of hemoglobin ≥ 11.5 g/dL for non-African American subjects or ≥ 11.0 g/dL for African American subjects in the previous month is required for the frequent sampling protocol. If the overnight admission is scheduled to occur greater than 3 months after screening, then the safety labs (complete blood count, comprehensive metabolic panel) will be repeated at this time.

Day 0: First inpatient admission

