Assessment of the sensitivity of the hypothalamic GnRH pulse generator to estradiol and progesterone inhibition in early pubertal girls (JCM026)

0700, 1500, and 2300 hr to achieve mean plasma concentrations over the range of 2-8 ng/ml for seven days. Each subject will be instructed to eat a small snack with the medication. It has been observed that the absorption of progesterone is influenced by the presence or absence of food. Subjects will continue their iron supplementation.

Days 3, 5: Outpatient blood draws

On study day 3, subjects will have blood drawn at 0900 or 1700 hr (two hours after the 0700 or 1500 hr progesterone dose) to check serum estrogen and peak progesterone levels. On study day 5, subjects will have blood drawn at 0900 or 1700 hr (two hours after the 0700 or 1500 hr progesterone dose) to check serum estrogen, peak progesterone levels, and hematocrit/hemoglobin. For the second admission to continue, subject must have a hemoglobin ≥ 11.0 g/dL for African American subjects or ≥ 11.5 g/dL for non-African American subjects.

Day 7: Second inpatient admission

The second inpatient admission will begin on day 8. The procedure will be identical to the first inpatient admission.

Follow-up

Subjects will discontinue estrace, progesterone, and iron after the completion of the second inpatient admission. Follow-up questionnaires and/or phone interviews will be completed by the subjects 3, 6 and 12 months after the study asking about the onset and frequency of menses and changes in hirsutism. During these interviews, we will specifically address whether pre-menarchal girls had a withdrawal bleed following the study, and if so, whether or not they subsequently continued menstruating. Whenever possible we will also see the patients on 2-3 occasions during the 12 months to obtain blood for T, DHEA-S, E₂, and P measurements (depending on cycle stage).

If a potential subject does not meet the inclusion/ exclusion criteria will you repeat any of the screening procedures/ tests? Yes

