If yes, please explain. Patients with elevated 17-OHP on screening will be referred to their pediatricians for further testing to rule out congenital adrenal hyperplasia. They will only be able to continue with the study if the have documented normal 17-OHP levels following cotrosyn stimulation. Additionally if safety labs are abnormal during screening (e.g., abnormal liver tests, abnormal TSH), subjects will be asked to return once for repeat (confirmatory) labs to exclude lab error. Repeat testing will generally occur within one month of the original screening lab draw. If exclusionary lab values are confirmed on such repeat testing, subjects will be excluded from participation. The exact amount of blood drawn will depend on the labs being repeated, but the total amount of blood drawn will not exceed 5 ml.

If clinically meaningful results are obtained during the course of the study, explain how you will notify the participant.

We will contact the custodial parent(s) via phone and make general recommendations (e.g., follow-up with the subject's primary care physician). We will generate a letter to the primary care physician (with a copy to the subject and her parent[s]) detailing the clinically meaningful results and associated findings of relevance.

Assessment of the sensitivity of the hypothalamic GnRH pulse generator to estradiol and progesterone inhibition in early pubertal girls (JCM026)

What treatments, normally used, will be omitted for the study?

Not applicable as these are normal, healthy subjects.

Will any of the treatments/ procedures be done for research purposes only? Yes

If yes, describe: All procedures are being done for research purposes only.

What details of the study are best kept secret from the participants?

None of the details of the study will be kept from the participants. Study participants and their parents will be advised of any and all aspects of the study. They will have ready access to their individual results after the data has been analyzed, and they may contact us to find out the results of the entire study once it has been completed.

Taping/Photography-N/A

Payment

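### Iron stops when the second admission ends, even if the prescribed 30-day course is unfinished, so girls admitted early in the course get fewer than 30 days

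*Combined protocol and SAP*

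**What the plan says.** The iron instructions are spread over several sections of the combined protocol and SAP.

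- **Outpatient Screening.** Once the screening tests show that a girl is eligible, she receives iron "for 30 days to help prevent anemia during and after the study". On timing: "The admission can take place any time during or after the iron supplementation". No minimum lead-in is set.
- **Day 1: Study medications.** Between the admissions, "Subjects will continue their iron supplementation".
- **Follow-up.** "Subjects will discontinue estrace, progesterone, and iron after the completion of the second inpatient admission". Nothing is said about a course still running.
- **Data and Safety Monitoring Plan, section 2.2.** Iron is listed among the safety measures and prescribed to all participants, with a dose but no duration.

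The last scheduled hemoglobin is on study day 5, and it must meet the threshold ("For the second admission to continue, subject must have a hemoglobin" at or above the stated level). Blood taken during follow-up is for hormones only and is drawn where possible. Section 3.6 records adverse events to 30 days after study drug but schedules no blood test.

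**The concern.** The Outpatient Screening text fixes the length of the course at 30 days. The Follow-up text fixes its end by a visit. The two agree only if the first admission comes late enough in the course, and the protocol does not require that. Staff who follow the Follow-up instruction would take a girl off iron that the screening instruction says she should still be taking, and section 2.2 gives no duration that would settle it.

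The participants are healthy children with no individual benefit. Section 2.1 lists anemia from frequent sampling as an expected risk, and iron is one of the listed protections. Where the course is cut, the cut falls just after the last large blood draw, with no hemoglobin scheduled afterwards. What is at stake is the completeness of a safety measure. LH pulse frequency, the sample size and the ANCOVA are not touched.

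**Working it through.** **Inputs.** Course length: 30 days (Outpatient Screening). Day 0 is the first admission. The second admission starts on day 7 by its heading and on day 8 by the text beneath it. It is overnight, with a last draw at 0700 hr, so it ends on day 8 or day 9.

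**Iron days taken by the stop point.** Let *a* be the iron-day on which the first admission falls, with the first dose on iron-day 1. Days taken = *a* + 8 or *a* + 9. Days not taken = 30 minus that, if positive.

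| First admission on iron-day | Days taken | Days not taken | Share of course not taken |
|---|---|---|---|
| 1 | 9-10 | 20-21 | 67-70% |
| 7 | 15-16 | 14-15 | 47-50% |
| 14 | 22-23 | 7-8 | 23-27% |
| 21 | 29-30 | 0-1 | 0-3% |
| 22 | 30-31 | 0 | 0% |

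The course is complete if *a* + 8 ≥ 30, so *a* ≥ 22 (day-7 start), or if *a* + 9 ≥ 30, so *a* ≥ 21 (day-8 start). This counts a dose on the morning of discharge. If the last dose is the evening before, each cutoff moves one day later.

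**Who could be affected.** Let *D* be days from screening to first admission and *s* be days from screening to the start of iron. Iron follows eligibility, so *s* ≥ 0, and *a* = *D* − *s* + 1. The course is cut on both visit calendars when *a* ≤ 20.

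- *D* ≤ 19: *a* ≤ 20 whatever *s* is, so the course is cut.
- *D* = 30: cut if *s* ≥ 11, since 30 − 11 + 1 = 20.
- *s* = 0-7 (assumed) and *D* = 30-60: *a* runs from 30 − 7 + 1 = 24 to 60 − 0 + 1 = 61, so no course is cut.
- *s* = 30 (assumed, a girl whose labs are repeated) and *D* = 30-60: *a* runs from 1 to 31, so some courses are cut.

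The third case fits the usual timeline: "Participants generally begin the main part of the study within 1-2 months of the screening visit". The fourth can arise because "Repeat testing will generally occur within one month of the original screening lab draw". The screening text also repeats a test only "If overnight admission is scheduled to occur greater than one month after the most recent hemoglobin", which allows an earlier admission without showing that it is common. The documents do not say how girls divide among these cases.

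**Blood drawn just before the stop.** Sampling every 10 minutes from 1900 to 0600 hr gives 67 samples.

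- If the larger samples replace small ones: 61 × 0.75 + 6 × 2.5 + 3.0 = 63.75 mL.
- Upper bound, if they are additional and one more is taken at 0700 hr: 67 × 0.75 + 7 × 2.5 + 3.0 = 70.75 mL.

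Before waste, this is 63.75/216.5 = 29% to 70.75/216.5 = 33% of the stated total of 216.5 mL.

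**The case against.** The best reply is that the cut may seldom happen. If iron starts promptly and admission is 30-60 days after screening, every girl finishes. The large losses need admission in the first week of iron, which the text permits but does not describe as usual. The repeat-lab case covers only girls whose abnormal safety labs clear on retest. This stands, and it limits the point to a minor one.

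Two further limits also stand. Girls with low hemoglobin at screening are offered a separate 60-day course and must reach the threshold before they proceed, so the day counts above understate their total iron. And the stop applies on completing the second admission. A girl who drops out, or who does not meet the day-5 hemoglobin threshold, never reaches it, and her 30-day prescription still governs. A reader might infer that every participant is told to stop early, but the text does not say so.

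A reader might also infer that having no iron planned after the second night is an error in itself, because the stated purpose reaches past the study. The documents do not support that. The phrase gives the aim of preventing anemia; it does not set a dosing period, and iron taken before and between admissions may still serve that aim afterwards. For the same reason there is no ground for requiring longer iron in girls admitted late in the course or after it.

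What the reply does not remove is the conflict between the two instructions for a girl admitted early, which the protocol expressly allows.

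**Conclusion.** The point holds as a minor safety and consistency matter. For a girl who completes both admissions and was first admitted before about iron-day 21-22, the stop instruction overrides the 30-day course. In the extreme case, admission on iron-day 1, she takes 9-10 of the 30 days.

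This rests on reading the Follow-up instruction as written and on the second admission ending on day 8 or 9. The one-day range comes from the protocol's own day-7 and day-8 wording. The number of girls affected is unknown and may be small.

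It would go too far to conclude that anemia will follow. The documents do not show it, and three protections remain: the cap of 7 cc/kg in 8 weeks, the 31 kg weight floor, and the day-5 hemoglobin requirement, which comes after the first night's loss. The primary analysis is unaffected.

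**What to change.** Under Follow-up, take iron out of the stop instruction. Suggested wording: Estrace and progesterone stop when the second admission ends; iron is taken until the 30-day course is complete, if it is not complete already.

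This raises the shortest course among girls who complete both admissions from 9-10 days to 30. A girl admitted on iron-day 1 gains 20-21 days, on iron-day 7 she gains 14-15, and on iron-day 14 she gains 7-8. Girls admitted from iron-day 22 on see no change, and the Outpatient Screening text can stay as it is.

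The cost is a one-sentence amendment and matching subject instructions, with no added visit or blood draw. At most, a girl takes 20-21 more days of iron already prescribed at screening: 20-21 tablets at 36 kg or less (once daily) or 40-42 above 36 kg (twice daily). The downside is the nausea and constipation already listed as risks of iron.

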2.1 What risks are **expected** due to the intervention in this protocol?

Expected: is identified in nature, severity or frequency in the study documentation (protocol, consent, Investigator Brochure, package insert etc) is considered an expected.

Risk associated with frequent blood sampling:

Expected Risks related to study participation-	Frequency		
volume of blood drawn	Please pick one frequency from each box below		
• Significant anemia related to frequent	Occurs frequently,		
blood sampling (hematocrit $< 30\%$)	Occurs infrequently		
	Occurs rarely		
	Frequency unknown, but likely to be very rare		
• Mild anemia (hematocrit < 36%)	Occurs frequently,		
related to frequent blood sampling	Occurs infrequently		

Assessment of the sensitivity of the hypothalamic GnRH pulse generator to estradiol and progesterone inhibition in early pubertal girls (JCM026)

Frequency unknown	Occurs rarely
-------------------	---------------

Risk associated with micronized progesterone suspension:

Expected Risks related to study participation-	Frequency		
micronized progesterone			
• GI upset (nausea, abdominal bloating,	Occurs frequently,		
diarrhea)	Occurs infrequently		
	Occurs rarely		
	Frequency unknown, but likely to be very rare		
• CNS effects (sleepiness, headache,	Occurs frequently,		
dizziness, fatigue, emotional lability,	Occurs infrequently		
irritability)	Occurs rarely		
•	Frequency unknown		
• Mild, short-lived vaginal bleeding	Occurs frequently,		
shortly after ingestion	Occurs infrequently		
	Occurs rarely		
	Frequency unknown		

Risk associated with estradiol:

Expected Risks related to study participation.	Frequency		
• GI upset (nausea, abdominal bloating, diarrhea)	 ☐ Occurs frequently, ☑ Occurs infrequently ☐ Occurs rarely ☐ Frequency unknown 		
Breast Tenderness	Occurs frequently, Occurs infrequently Occurs rarely Frequency unknown		
• Deep vein thrombosis	 Occurs frequently, Occurs infrequently Occurs rarely Frequency unknown, however occurs very rarely with long-term estrogen use (as with oral contraceptive pills), so would expect to be exceedingly rare with the short term administration in this protocol 		

Risk associated with IV needle placement:

Expected Risks related to study participation- IV placement	Frequency		
Infection at needle site	 Occurs frequently, Occurs infrequently Occurs rarely Frequency unknown, but likely to be very rare 		
• Bleeding at needle site	 ☐ Occurs frequently, ☐ Occurs infrequently ☑ Occurs rarely 		

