Assessment of the sensitivity of the hypothalamic GnRH pulse generator to estradiol and progesterone inhibition in early pubertal girls (JCM026)

Frequency unknown
Occurs frequently,
Occurs infrequently
Occurs rarely
Frequency unknown
Occurs frequently,
Occurs infrequently
Occurs rarely
Frequency unknown
Occurs frequently,
Occurs infrequently
Occurs rarely
Frequency unknown

Risk associated with iron supplementation

Expected Risks related to study participation-	Frequency		
iron supplementation	Please pick one frequency from each box below		
• nausea	Occurs frequently,		
	Occurs infrequently		
	Occurs rarely		
	Frequency unknown		
constipation	Occurs frequently,		
-	Occurs infrequently		
	Occurs rarely		
	Frequency unknown		
dark or black stools	Occurs frequently,		
	Occurs infrequently		
	Occurs rarely		
	Frequency unknown		

Risk associated with EMLA cream (topical lidocaine and prilocaine, used to alleviate pain): The risks of lidocaine and prilocaine in general may include (frequency not defined) hypotension, angioedema, shock, hyperpigmentation, erythema, itching, rash, burning, urticaria, burning, stinging, edema bronchospasm, and hypersensitivity reactions. However, in the case of topical lidocaine/prilocaine use, the non-dermatologic adverse events mentioned above would be extremely unlikely unless large amounts of topical lidocaine/prilocaine were used (allowing significant systemic absorption).

Risk regarding wrist actigraphy: There are no known risks associated with the use of wrist actigraphy.

Risk of not being able to take hormonal medications: Fertility in premenarcheal girls is exceedingly unlikely. Thus, the risk of pregnancy related to inability to take hormonal birth control medication is virtually absent.

- 2.2 List by bullet format a summary of safety tests/procedures/observations to be performed.
 - Sterile technique will be used.
 - Before participation in the study, all participants will be required to have a normal hemoglobin (≥ 11.0 g/dl for African American subjects or ≥ 11.5 g/dL for non-African American subjects). Hemoglobin levels will be measured prior to every admission, and the admission will only continue if the

Assessment of the sensitivity of the hypothalamic GnRH pulse generator to estradiol and progesterone inhibition in early pubertal girls (JCM026)

hemoglobin level is ≥ 11.0 g/dl for African American subjects or ≥ 11.5 g/dL for non-African American subjects.

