- Blood loss will be carefully recorded and limited to a maximum of 7cc/kg (10% of estimated total blood volume) in 8 weeks. A total of 216.5 ml of blood will be drawn during the study (including estimated waste from frequent blood draws). Therefore, girls weighing less than 31 kg will not be able to participate. Iron supplementation (325 mg once or twice a day dependent on weight) will be prescribed to all participants.
- β -hCG levels will be measured at screening and prior to each admission; if the β -hCG is positive, the study will be discontinued.
- Topical lidocaine and prilocaine (EMLA) cream may be used to lessen pain associated with IV needle insertion.
- 2.3 Check the criteria below under which an INDIVIDUAL SUBJECT'S study treatment or study participation would be stopped or modified

At subject, PI or sponsor's request

Treatment would be stopped if the subject had a Serious adverse event deemed related to study

The study would be stopped in the patient has a positive pregnancy test or a hematocrit <36 and hemoglobin <12 prior to any of the 4 admissions.

2.4 Check the criteria under which THE ENTIRE STUDY would need to be stopped. These are called stopping rules for early termination of the entire study.

⊠Per IRB, PI, DSMB, or sponsor discretion

 \bigcirc Other: If there are an excessive number of unexpected adverse events that significantly alter the risk/benefit ratio for the study, the study will be terminated. All adverse events will be evaluated both individually and cumulatively by the study team and principal investigator as they arise, allowing for timely decisions regarding study continuation/termination.

- 2.5 Describe the criteria for breaking the blind/mask 🖾 NA Not blinded/masked
- 2.6 How will subject withdrawals/dropouts be reported to the IRB prior to study completion?☑ IRB-HSR continuation status form

3. Adverse Event / Unanticipated Problem Recording and Reporting

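### Two different hemoglobin/hematocrit limits decide whether a girl enters a sampling night, and the iron instructions disagree on when the course ends

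*Combined protocol and SAP*

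**What the plan says.** **The gate.** Inclusion/Exclusion Criteria, Outpatient Screening, Days 3, 5: Outpatient blood draws, and item 2.2 of the Data and Safety Monitoring Plan all use one limit. On day 5 blood is taken "to check serum estrogen, peak progesterone levels, and hematocrit/hemoglobin", and then: "For the second admission to continue, subject must have a hemoglobin ≥ 11.0 g/dL for African American subjects or ≥ 11.5 g/dL" for other girls. Item 2.2 applies the same figures to both nights: "Hemoglobin levels will be measured prior to every admission".

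**The stop rule.** Item 2.3, on stopping an individual girl, names a positive pregnancy test or "a hematocrit <36 and hemoglobin <12 prior to any of the 4 admissions". It has no race split. The protocol describes two admissions.

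**Iron.** Outpatient Screening gives eligible girls "oral iron supplementation at a dose of 1-2 mg/kg for 30 days to help prevent anemia during and after the study", and adds: "The admission can take place any time during or after the iron supplementation". The Follow-up paragraph says: "Subjects will discontinue estrace, progesterone, and iron after the completion of the second inpatient admission".

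**After the second night.** No hemoglobin or hematocrit is scheduled. Follow-up blood, taken where feasible, covers four hormones only. Item 2.1 lists mild anemia, defined as hematocrit below 36%, as an expected risk of the sampling. Item 2.2 caps blood loss at 7 mL/kg in 8 weeks and puts the study total at 216.5 mL.

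**The concern.** Before each sampling night staff must decide whether a healthy child goes on, and the current text gives two tests that can return different answers. A non-African American girl with hemoglobin 11.7 and hematocrit 35 meets the gate and also meets the stop criterion. No sentence says which governs, so following one rule can look like a violation of the other. The choice can also decide whether she becomes one of the 10 completers sought from 16 enrolled.

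The iron text has a similar fault: one section aims the course partly at the time after the study, and another ends it at discharge. A smaller matter is that the second night's blood is all drawn after the last hemoglobin check, so nothing scheduled shows where a girl ends.

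**Working it through.** **1. The plan's own figure.** 216.5 mL ÷ 7 mL/kg = 30.93 kg, which reproduces the 31 kg minimum weight. At 31 kg the cap is 31 × 7 = 217.0 mL, leaving 0.5 mL spare.

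**2. The two rules side by side.** Gate: continue only if hemoglobin (Hb) ≥ 11.5, or ≥ 11.0 for African American girls. Stop rule: stop if hematocrit (Hct) < 36 and Hb < 12.

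| Hb / Hct | Girl | Gate | Stop rule |
|---|---|---|---|
| 11.7 / 35 | non-African American | met | stop |
| 11.2 / 35 | African American | met | stop |
| 11.4 / 36 | non-African American | barred | not stopped |
| 10.9 / 36 | African American | barred | not stopped |

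**3. Width of the disagreement.** The width depends on the ratio r = Hct/Hb, which the protocol does not give; 2.9 to 3.1 is assumed. The stop rule acts when Hb < min(12, 36/r).
- r = 2.9: 36/2.9 = 12.41, so the limit is 12.
- r = 3.0: 36/3.0 = 12.
- r = 3.1: 36/3.1 = 11.61.

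Girls who meet the gate but are stopped therefore have Hb 11.5 to <12 (11.0 to <12 if African American) at r up to 3.0, narrowing to 11.5–11.6 (11.0–11.6) at r = 3.1. The reverse case needs a higher ratio: above 36/11.5 = 3.13, or 36/11.0 = 3.27 for African American girls.

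**4. Iron.** If a girl starts on day 0, the morning after a second admission on day 7 or day 8 (the heading and the text beneath it differ) is 8–9 days later. She forgoes 30 − 8 = 22 or 30 − 9 = 21 days. If she starts at least 22 days before day 0, she forgoes none.

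**5. Blood drawn after the last check.** Sampling every 10 minutes from 1900 to 0600 gives 660/10 + 1 = 67 draws; 0700 makes 68.
- Six 2.5 mL samples replacing small ones: 62 × 0.75 + 6 × 2.5 + 3.0 = 64.5 mL (29.8% of 216.5).
- Seven replacing: 61 × 0.75 + 7 × 2.5 + 3.0 = 66.25 mL (30.6%).
- Seven added to the small ones: 68 × 0.75 + 7 × 2.5 + 3.0 = 71.5 mL (33.0%).

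These exclude waste. If all other draws total only 20 mL (assumed) and waste takes the rest, a night reaches (216.5 − 20)/2 = 98.25 mL.

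**6. Fall at 31 kg.** Blood volume is 31 × 70 = 2,170 mL, the 70 mL/kg being implied by the protocol's equating 7 mL/kg with 10%. Assuming simple dilution and no regeneration, from Hb 11.5:
- 66.25/2,170 = 3.05%, a fall of 0.35 g/dL.
- 98.25/2,170 = 4.53%, a fall of 0.52 g/dL.

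Lowest end values over that range are 11.6–11.5 from 12.0, 11.2–11.0 from 11.5, and 10.7–10.5 from 11.0.

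**The case against.** The strongest reply is that both limits are restrictions. The gate is worded as a condition that must be met, so the two can be applied together, and a girl failing either is stopped. That is workable, but no sentence says it. At r up to 3.0 it would also leave the gate and its race allowance with no effect before an admission, because every girl with Hb below 12 would already be stopped. The count of four admissions suggests that item 2.3 was carried over from another protocol. That is an inference, but it points to an editorial fault with a simple cure.

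On the missing late test the plan's defense is good. Loss is capped, iron is given, and day 5 shows each girl's response to a first night of equal volume. Adverse events are recorded to 30 days, though a fall without symptoms would not surface that way.

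Three stronger readings are tempting, and the documents do not support them:
- A reader might infer that a girl close to the gate drops below hematocrit 36% unseen. At r = 3.0, Hb 11.5 means hematocrit 34.5, so she is already below that line and day 5 shows it. A new crossing at 31 kg needs a day 5 hematocrit from 36.0 up to 36/(1 − 0.0305) = 37.1, or 36/(1 − 0.0453) = 37.7. That corresponds to Hb of about 12.0–12.6.
- A reader might think it enough to say that the stricter rule governs. Step 2 shows that neither is stricter throughout.
- A reader might suppose that every girl's iron course is cut short. The main study usually starts 1–2 months after screening, so many may have finished it.

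**Conclusion.** The conflict between the entry limits is established from the current text and needs no assumption; only its width depends on the hematocrit-to-hemoglobin ratio. The iron instructions also disagree, at a cost of 0 to about 22 days of a 30-day course depending on when a girl starts. The absence of a hemoglobin check after the second night is a fact but of low severity: the fall is about 0.35–0.5 g/dL for the lightest eligible girl, the upper end resting on assumed waste.

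The protocol gives no distribution of weight or of day 5 values, so the number of girls in the disputed range is unknown. Nothing here supports a claim of expected harm. The LH endpoint, the sample size and the planned analysis do not change.

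**What to change.** 1. **Entry limits.** Replace the blood-count criterion in item 2.3 with the gate: stop if hemoglobin is below 11.5 g/dL, or below 11.0 for African American girls, before either of the two admissions. This costs one sentence and uses a measurement already required before both nights. It does admit girls whom item 2.3 now stops: at r = 3.0 the lowest end value at 31 kg moves from about 11.5–11.6 g/dL to 11.0–11.2, or 10.5–10.7 for African American girls. If the sponsor wants more protection, state instead that a girl failing either rule is stopped, and correct the number of admissions. The cost is then some lost completers.

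2. **Iron.** State that a girl with days left in her 30-day course finishes it after the second admission. For some girls this means up to about 22 more days of the listed side effects (nausea, constipation, dark stools). It needs no blood.

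3. **Optional.** Run a micro-volume hemoglobin/hematocrit on blood already taken at 0700 of the second admission. If hemoglobin is below the same 11.5/11.0 gate, use the existing procedure for clinically meaningful results. With 0.5 mL spare at 31 kg, it must come from existing volume. One hour after ten-minute sampling ends it may understate the full fall, and the protocol should say so. The cost is one routine assay per girl and no added visit.
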